10. DATA COLLECTION AND QUALITY ASSURANCE

[figure not shown]
10.1 Data Collection Forms

Initial screening data will be directly entered by potential study participants via a web-based survey supplied by the DCC. Phone-based screening data and in-person/video-conference screening data obtained at the in-person/videoconference visit will be entered directly into the study portal by research staff at the sites to confirm study eligibility. For consented participants, protected health and contact information will be stored in a separate limited-access REDCap database and no research personnel will have data export rights in this database. Data collected as a part of the research study protocol database will be stored in a completely separate database, linked by study ID. A procedure/visit case report form will be filled out by research staff for every study-related visit and electronically entered directly into the web-based portal. Electronic web-based surveys will be sent to study participants on a monthly basis, with computer-assisted telephone interviewing or mailed surveys as a parsimoniously used back-up in cases where follow-up may be challenging. Printable CRFs will be made available for every study assessment.

10.2 Data Management

Data management in the LBP project will be almost exclusively web-based. The UWA DCC will support an https-secured web page (www.PACBACK.ORG) that provides a centralized location for public information about the project for potential subjects, investigators, and institutional agencies. The web page will contain a link to the project portal. Study personnel will log on to the private portal on the study web page with individual Shibboleth-based user names and passwords to securely perform study data management activities. Shibboleth is a standards-based, open source software package for web single

sign-on across or within organizational boundaries. An overview of the DCC responsibilities and data management system is presented below.

Study Integration: The UWA DCC team has extensive experience developing Application Programming Interfaces (APIs), which allow multiple software programs to seamlessly interact and communicate with one another in a simple and intuitive interface. The web portal API will serve as the wrapper for all data management tools and software utilized in the LBP project, including: study ID assignment, screening, centralized image storage (if needed), prospective data collection forms and surveys, and study operations reporting. Screening and eligibility will be determined centrally through the portal and all subjects screened under the LBP trial protocol will be assigned a sequentially generated study participant ID. The DCC will maintain an additional REDCap database to centrally and securely store identifiable patient information, separating patient contact information from research study data. For each REDCap database, the DCC will use distinct data access groups for clinical recruitment sites.

Electronic Data Capture: The UWA DCC supports its own installation of REDCap, which is software specifically designed for electronic data capture that we have used successfully in several multi-site clinical trials. REDCap features include differentiated user roles and privileges, password and user authentication security, electronic signatures, SSL encryption, and comprehensive auditing to record and monitor access and data changes (<http://www.project-redcap.org/software.php>). REDCap will serve as the architectural backbone for all data captured prospectively in this study, with all data linked by study subject ID. The web-based data management portal allows for four participant contact methods: research coordinator data entry; electronic survey; computer-assisted telephone interviewing (CATI); or Short Message Service (SMS) text message. All survey modalities are customized to incorporate project logos and information to increase participant recognition and response rate. Furthermore, surveys may be

distributed on any time schedule (e.g., monthly for pain and disability), and in any designated survey format.

Access and Security: The DCC will invite each research staff member at the clinical recruitment sites to obtain a University of Washington NetID, which will be required to gain access to the secured study for screening, randomization, and data entry. Research staff will be grouped into data access groups whereby study participant data will be separated by site, as appropriate. The clinical recruitment sites are responsible for scheduling patient follow-up visits. REDCap databases are stored on a secure electronic server with username and passwords login for individual users and will be backed up nightly. The REDCap servers are virtual machines (VMs) located on UW DCC hardware in a secure server room. Our server room meets the technical requirements for HIPAA compliance and hosts servers that do contain PHI. Storage for all study data is backed by (2) dedicated Network Appliance FAS2050 storage appliances. The filer provides highly fault tolerant storage using large RAID volumes, on-line hot-spare drives, and built-in, proprietary 'snapshot' file system technology that automatically creates hourly, daily, and weekly on-line backups of modified files.

10.3 Quality Assurance

10.3.1 Training

Training: Before any clinical recruitment site may begin recruitment for this study, the DCC will provide two training sessions on the data management system for all research staff. The first training session will be a GoToMeeting virtual tour of the data system conducted by the DCC protocol operations specialist; the second training is a GoToMeeting virtual training session where research staff are observed interacting with the system by a UWA DCC staff member and are required to demonstrate proficiency in key data management steps (screening, randomization, data entry, documentation of AEs, data management protocol compliance, etc.). As with most studies, there will likely be turnover in recruitment site personnel necessitating a process for ongoing training. The DCC will create data management system training videos that covers the material of the first training session. All new research staff will be required to view the suite of training videos and then complete a second virtual training session with the DCC protocol operations specialist prior to being given a log-in and access to the study portal. Detailed communication about protocol and case report forms changes will come through the DCC through Basecamp (www.basecamp.com) notifications, a program used to facilitate project management and study-wide communication. The DCC will additionally develop a question-by-question (QxQ) document that outlines in detail the intent of each research staff-facing CRF question and response.

10.3.2 Quality Control Committee

Missing data reporting and other customized reports will be developed by the DCC in collaboration with the CCC and recruitment team in order to facilitate efficient work-flow and high-quality data capture. A subset of key personnel from the DCC and CCC will serve as an operations committee and review quality control reports on a weekly or biweekly basis, though quality control reports will be made available on a daily basis. CRF-specific follow-up rates will be tabulated on a nightly basis and reviewed during the weekly check-in meeting with each clinical recruitment site. Nightly, the DCC will generate graphs that monitor CRF-specific follow-up rates over time as well as data quality trigger rates over time to prospectively monitor potential issues that may develop gradually or acutely over time. A data query resolution dashboard will be available to each site on a continuous basis. In similar studies, we have found that establishing a fixed-day for a monthly review of all unresolved queries is an adequate balance of time to resolution and alert fatigue.

10.3.3 Metrics

For each monthly follow-up survey, we aim to achieve an 85% or higher follow-up rate. We will utilize a combination of web-based survey, telephone and text-based outreach, and mailed surveys to achieve maximal survey response – especially at the 6 and 12-month follow-up time points. Survey completion rates will be primarily based upon the completion of pain and functional outcome measures, but the DCC will additionally tabulate follow-up by each instrument to monitor and evaluate survey burden.

Loss to Follow-Up: Participants are considered loss to follow-up if a participant

1. Dies, or they
2. Missed 3 consecutive monthly surveys, and
3. Missed 4 consecutive weekly surveys (~1 consecutive month), and
4. 3 email/text auto or manual reminders and 3 phone calls result in no response from the participant

When criteria 2-4 are met, the DCC will stop (turn off) the weekly and monthly surveys with the exception of the 6 and 12 month surveys (primary outcome). Study staff will contact participants prior to request they provide data at these time points.

Participants' status may be adjusted if the participant contacts the study and begins participating in data collection activities.

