3.2 Primary and secondary outcomes

Primary and secondary outcomes will be collected predominantly using web-based self-report tools (for details see section 6.1 Schedule of Evaluations and section 10 Data Collection & Quality Assurance).

Primary effectiveness outcome measures are: (1) prevention of cLBP that is impactful at 10-12 months follow-up (LBP impact from the PROMIS-29 Profile v2.0); (2) average pain intensity over 12 months post-randomization (pain, numerical rating scale); (3) average low back disability over 12 months post-randomization (Roland-Morris Disability Questionnaire). Secondary outcomes include: recovery, PROMIS-29 Profile v2.0 measures to assess pain interference, physical function, anxiety, depression, fatigue, sleep disturbance, and ability to participate in social roles and activities. Other patient-reported measures include LBP frequency, medication use, healthcare utilization, productivity loss, STarT Back screening tool status, patient satisfaction, prevention of chronicity, adverse events, and implementation measures. Objective measures include the Quebec Task Force Classification, Timed Up & Go Test, the Sit to Stand Test, and the Sock Test assessed by clinicians blinded to the patients' intervention assignment.

Prevention of chronic LBP will be measured using the patient-rated LBP impact measure described by the NIH RTF⁷³ which is a quantitative measure derived from subsets of the PROMIS-29. It is scored on a scale of 8-50 (8-27: Mild; 28-34: Moderate and >34: Severe). We will measure LBP Impact on a monthly basis using the area under the curve for Month 10-12 as the primary endpoint.

There is evidence on reliability, validity, and responsiveness and its prognostic value to support the use of the impact measure. (Dutmer 2019)

Important note: The chronic LBP impact measure was collected as a secondary outcome measure from the start of the trial but was adopted as a primary outcome in July 2021 with approval from the trial DSMB and by NIH. At the time of the change in primary endpoint less than 25% of the total participants had been recruited into the trial. Under the supervision of the data coordinating center no interim analysis was planned or conducted and none of the investigators have had access to outcomes data.

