9. STATISTICAL CONSIDERATIONS

Modifications to Statistical Analysis Plan Regarding the Sample Size and Power

(edited February 2023)

In consultation with NCCIH program staff and the DSMB in December 2022 we have modified the target enrollment to n=1000 participants (reduced from original n=1180). Our rationale for the modification is based on alignment with our updated primary outcome on chronicity. We have conducted extensive evaluation of power to detect meaningful effects using the LBP-Impact measure and our other primary outcomes. We have determined that it is appropriate to reduce the target sample size.

Modifications to Statistical Analysis Plan Regarding Primary Analysis and Treatment of Multiple Comparisons

(edited September 2022)

The trial initially had three main effectiveness objectives: (1) prevention of chronic LBP at twelve months; (2) recovery from acute/sub-acute LBP at six months; (3) Average of pain and disability over twelve months. In 2021, the NIH statistician overseeing the trial raised the question of the adequacy of the planned adjustment for multiplicity given the trial's three main effectiveness objectives and accompanying four primary outcome measures. In response to this concern, the lead investigators recommended the recovery objective be changed to a key secondary outcome. Early in the conduct of the trial it was decided and approved as a protocol change to include patients that had an acute aggravation of ongoing LBP, if the ongoing pain was not rated as severe in the month prior to the aggravation. This protocol change substantially lowers the proportion of patients that can be expected to recover according to our criteria (pain severity = 0 and RMD score ≤ 2). Given this change, the recovery outcome was less appropriate as a primary effectiveness objective and demoting it to a secondary outcome mitigates the concern of cross-objective control.

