- We have evaluated the impact on the power of our study subject to the potential for up to 240 subjects enrolled during restricted randomization. In our original protocol we focused sample size on obtaining adequate power for the Aim 1 chronicity endpoint assuming treatment relative risks of 0.70 (a 30% relative reduction), no interaction between treatments, and a control rate of 0.20. For this original scenario we used simulations to compute a power of 81% for either the overall SSM effect or the overall SMT effect. With partial randomization and an upper bound of n=240 subjects allocated during this period we obtain 78% power to detect an overall SSM effect and 77% power to detect an overall SMT effect. Therefore, the impact of altering the design to permit partial randomization is anticipated to have a minor reduction in power for our binary endpoints. In addition, the planned design will result in a minimum of n=30 per protocol pre-COVID subjects in the SMT and SSM+SMT groups combined with a full factorial randomization allocation of n=188 will permit a total of n=30+188=218 subject per group to evaluate mean differences in pain and disability scales across the four treatment groups. For MC and SSM groups we expect to have an upper bound of n=45 pre-COVID, n=120 partial randomization, and n=188 full factorial randomization subjects or n=45+120+188=354 total subjects per group. Our original balanced allocation would have produced n=1180/4= 295 subjects/group.

Statistical Analysis Plan

Introduction: A factorial trial is ideal when the two treatments under study are thought to act independently via different mechanisms.¹⁴⁶ Our interventions focus on a physical treatment approach (SMT) and a psychological intervention (SSM) for addressing acute LBP. A factorial design allows an efficient evaluation of each of these modalities using fewer subjects than would be required by separate trials. In addition, a crucial advantage of a factorial trial is the ability to evaluate whether the beneficial effects of each treatment modality combine in an additive, antagonistic, or synergistic fashion through evaluation of treatment interaction.¹⁴⁷

The trial was originally powered to detect meaningful differences in two dichotomous primary outcome measures, chronicity and recovery. These two outcomes are now secondary effectiveness measures.

Figure 9.1: The 2x2 factorial design (n=1000)

	SMT Intervention	No SMT Intervention

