SSM Intervention	SMT + SSM Group A	SSM only Group B
No SSM Intervention	SMT only Group C	Usual Medical Care Group D

For the 3 quantitative primary outcomes collected longitudinally, RMDQ, Pain NRS and LBP-Impact we will conduct detailed analysis of the four groups formed by the factorial design since we have excellent power for such endpoints with our revised sample size of 1000 subjects. However, McAlister et al.¹⁴⁶ comment that “the most powerful analysis of a factorial trial is performed at the margins” and we adopt such an approach for our secondary binary chronicity and recovery outcomes. We explicitly define the separate treatment effects for SMT and SSM as the overall or average treatment effect that is obtained from pooling comparisons over strata defined by the other treatment approach (i.e., the SMT treatment effect obtained by pooling over strata

with and without SSM). In particular, we define the parameter of interest as a linear combination (contrast) of parameters from an appropriate regression model that acknowledges the potential for SMT and SSM interaction. Therefore, our proposed analyses for binary outcomes do not make any additive assumptions and is quite generally valid for creating meaningful overall effect summaries. Furthermore, by collecting detailed outcomes and health care utilization through one year we can conduct thorough mediation analyses and careful evaluation of concomitant treatment.

Our statistical analysis plan focuses on the effectiveness evaluation detailed under the Primary Objective in the protocol. We also provide a plan for mixed methods analyses (qualitative/quantitative) associated with the Secondary Objective: implementation.

Primary Effectiveness Outcome # 1: prevention of cLBP that is impactful at 10-12 months follow-up (LBP Impact scale (min 8 - max 50) using mean from months 10-12). The LBP impact scale includes measures of pain intensity, pain interference, and physical function from the PROMIS-29 Profile v2.0) we will determine the effectiveness of SMT, SSM, and the combination of SMT+SSM relative to medical care (MC)

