LBP Impact Effectiveness Hypothesis: SMT alone will decrease the impact of low back pain with at least a moderate effect size of 0.3 standard deviations (Cohen's d). Similarly, SSM alone will decrease the impact of low back pain with at least a moderate effect size of 0.3 standard deviations. The combination SMT+SSM will lead to a stronger but not necessarily additive net reduction compared to the individual component interventions.

Design: As shown in Figure 9.1, we plan to enroll a total of 1000 subjects randomized to one of four treatment groups using a factorial design: medical care (MC); spinal manipulation therapy alone (SMT); supported self-management alone (SSM); and combined SMT+SSM.

LBP Impact Primary Analysis: Our primary analysis will compare each of the treatment groups to MC using an adjusted regression analysis. Specifically, Let Y_{ij} denote the primary outcome variable (average of LBP-Impact over months 10-12) for subject i in site j, and let $Site(2)$ be an indicator variable used to code the two recruitment sites. All analyses will adjust for site and the baseline risk status represented by $RiskGroup$ (0=medium risk; 1=high risk). In order to code the treatment groups we use the variables *SMT-Only* (0=no; 1=only spinal manipulation therapy), *SSM-Only* (0=no; 1=only supported self-management), and *SMT-and-SSM* (0=no, 1=both SMT and SSM). Given interruption by COVID-19 and an associated period of restricted randomization we will also adjust for this modified randomization using the variables *Period(k)* which will be an indicator for: 1=UG3 and UH3 through March 2020; 2=calendar period of restricted randomization; and 3=calendar period of resumed full factorial randomization. We will use an adjusted linear regression model with robust standard error to make inference regarding treatment groups using the following structure where X_{ij} denotes the covariates for subject i:

$$E(Y_{ij} | X_{ij}) = \beta_0 + \beta_1 \cdot Site(2)_j + \beta_2 \cdot RiskGroup_{ij} + \beta_3 \cdot SMT-Only_{ij} + \beta_4 \cdot SSM-Only_{ij} + \beta_5 \cdot SMT-and-SSM_{ij} + \beta_6 \cdot Period(2)_{ij} + \beta_7 \cdot Period(3)_{ij}$$

In the primary regression model the parameters of interest are:

β_3 = adjusted mean difference comparing SMT Only to UMC;

β_4 = adjusted mean difference comparing SSM Only to UMC;

β_5 = adjusted mean difference comparing combined SMT and SSM to UMC.

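### After a participant is flagged as lost to follow-up, only the month 6 and 12 surveys continue, so up to two of the three months in the LBP Impact primary endpoint are never sent

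*Combined protocol and SAP*

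**What the plan says.** Section 10.3.3 (Loss to Follow-Up) flags a participant who has missed three consecutive monthly surveys and four consecutive weekly surveys and has not answered three reminders and three calls. At that point "the DCC will stop (turn off) the weekly and monthly surveys with the exception of the 6 and 12 month surveys (primary outcome". For the two surveys that remain, "Study staff will contact participants prior to request they provide data at these time points". The way back is on the participant's initiative: their "status may be adjusted if the participant contacts the study and begins participating in data collection activities".

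The first primary outcome is defined in section 3.2: "We will measure LBP Impact on a monthly basis using the area under the curve for Month 10-12 as the primary endpoint". Section 9 repeats it, and the primary model takes as its dependent variable "the primary outcome variable (average of LBP-Impact over months 10-12) for subject i in site j".

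Section 9 also records that the trial's initial objectives included "1) prevention of chronic LBP at twelve months; (2) recovery from acute/sub-acute LBP at six months", and its Statistical Analysis Plan introduction says of dichotomous chronicity and recovery: "These two outcomes are now secondary effectiveness measures".

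The revision history dates the loss-to-follow-up definition to Version 5 (October 2019). Section 3.2 dates the adoption of LBP Impact as a primary outcome to July 2021.

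**The concern.** The surveys kept after flagging do not match the endpoint they should protect. Month 6 lies outside the LBP Impact window and month 12 is one of its three months. No section exempts months 10 and 11. The rule thus gives up the planned chance to collect up to two of the three component scores from the participants whose data are most at risk.

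A second gap affects even the month that is kept. Section 6.2.2 builds LBP Impact from nine items that include pain intensity. The same section leaves the pain-intensity question out of the PROMIS-29 because it is collected weekly, and the schedule in 6.1 lists LBP intensity at screening, at baseline and weekly. The weekly surveys are turned off after flagging, and the documents do not say whether the month 12 survey repeats the item.

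**Working it through.** **1. What is not sent, by month of flagging.** Flagging needs three consecutive missed monthly surveys, so month 3 is the earliest.

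| Flagged at month | LBP Impact months not sent | Endpoint months still sent after flagging |
|---|---|---|
| 3-9 | 10 and 11 | 12 |
| 10 | 11 | 12 |
| 11 | none | 12 |
| 12 | none | none left |

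**2. Volume.** The documents give no flagging rate. Assume 2-10% of 1000 are flagged by month 9: 20-100 participants, and 2 × 20 = 40 to 2 × 100 = 200 surveys not sent. If 10-25% of those participants would answer (assumed), the values recovered run from 2 × 20 × 0.10 = 4 to 2 × 100 × 0.25 = 50.

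**3. The plan's own power figure.** Section 9 gives about 300 participants each in MC and SSM, 200 each in SMT and SMT+SSM, 90% follow-up and a 3-df test at alpha 0.05. I take this as 180 evaluable per arm under four-arm randomization plus 90 each in MC and SSM in the restricted period (4 × 180 + 2 × 90 = 900), adjusted for period. For Sub-Additive 1 (0.25, 0.25, 0.35 SD):
- Four-arm part: the arm means 0, 0.25, 0.25, 0.35 average 0.2125 and have squared deviations summing to 0.066875; × 180 = 12.04.
- Restricted period: (90 × 90/180) × 0.25² = 2.81.
- Noncentrality 14.85, power 91.3%, against 91% in Table 9.1. All eight rows of the table reproduce within 2 points.

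**4. If month 12 alone stands in for the mean.** With between-month correlation r (assumed 0.5-0.9), the variance of one month relative to a three-month mean is 1/(r + (1−r)/3): 1.50, 1.25 and 1.07 at r = 0.5, 0.7 and 0.9. With flagged share f, the average inflation is (1−f) + f × ratio. If a share p of those flagged answers months 10 and 11, it becomes (1−f) + f × (p + (1−p) × ratio).

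| f, r | Inflation now | Power now | Gain, p = 10% | Gain, p = 25% | Gain, p = 100% |
|---|---|---|---|---|---|
| 2%, 0.9 | 1.0014 | 91.2% | 0.004 | 0.010 | 0.04 |
| 5%, 0.7 | 1.0125 | 90.9% | 0.04 | 0.09 | 0.37 |
| 10%, 0.5 | 1.05 | 89.8% | 0.15 | 0.38 | 1.49 |

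Gains are in percentage points of power. They assume that everyone flagged answers month 12.

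**5. If month-12-only participants are excluded instead.** Noncentrality scales with the number evaluable. For assumed shares s of the 900:
- s = 5%: 855 left, power 89.7%
- s = 10%: 810 left, power 87.9%
- s = 15%: 765 left, power 85.8%

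The loss is 1.6 to 5.5 points. With the fix, 900 × (1 − s(1−p)) remain. At s = 5% and p = 10% that is 859.5 and 89.9%; at s = 15% and p = 25% it is 798.75 and 87.4%. The fix therefore recovers about 0.2 to 1.6 points.

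**The case against.** The strongest reply is that the rule is a sensible landmark-month minimum for people who have stopped answering. Chronic LBP status, psychosocial mediators, satisfaction and STarT Back status are collected at months 6 and 12 and never at 10 or 11. Chronicity at both months and recovery at month 6 are key secondary outcomes. Section 8 sets a similar minimum (months 2, 6 and 12) for reluctant participants who have discontinued treatment. Extra contacts could also tire the participants whose month 12 response is wanted. All of this justifies keeping months 6 and 12. It does not explain leaving out months 10 and 11, since the rule already accepts that re-contacting non-responders is worthwhile.

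A reader might infer that the label is simply wrong, because it fits two outcomes that are now secondary. The documents do not support that. Average disability over 12 months is a current primary outcome built from monthly questionnaires, so months 6 and 12 both contribute to it. The revision dates are consistent with a rule that was not updated, but they do not prove it.

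It is also true that many of these data would be missing anyway, that section 9 plans multiple imputation and sensitivity analyses, and that every monthly survey carries an 85% follow-up target before flagging. No lead time is given for the contact before month 12, so it could happen to fall while month 11 can still be collected. The rule does not provide for that.

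**Conclusion.** The mismatch stands on current text: following the rule as written produces avoidable missing data on a primary endpoint. Severity is minor to moderate.

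A reader might infer that the endpoint is lost for flagged participants, that the trial is underpowered, or that the result is biased. None of these follows. Month 12 is still requested, nothing here estimates bias, and the power figure in Table 9.1 is not in dispute.

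The size depends on things the documents do not supply: the share flagged, the share who would answer, the between-month correlation, and how a month 10-12 average is formed from one month. A gain below 0.4 points is not an upper bound, because it holds only if month 12 alone would be used as the mean. Under exclusion the loss is larger, and the fix returns only the part due to those who answer. The case for the change rests on less missing data rather than on power.

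**What to change.** In section 10.3.3:
- Retain the month 6, 10, 11 and 12 surveys after flagging.
- Include the pain-intensity item in the month 10, 11 and 12 surveys. Without it, the added surveys may not yield an LBP Impact score while the weekly surveys are off.
- Apply the same staff contact before each retained survey.
- Reword the label so that months 10-12 are named as the LBP Impact primary endpoint.

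The cost is protocol wording, a survey-schedule setting, and two extra short surveys and contacts for a minority who have already stopped responding. The change helps only participants not yet past month 10 when it takes effect (month 11 for the second survey). The corrected label is useful regardless.
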